8.5 Analysis Sets

There will be two analysis sets; the safety analysis set and the microbiology analysis set.

The safety analysis set will be defined as those subjects enrolled and have received any amount of C16G2 Varnish or Placebo.

The microbiology analysis set will be comprised of two subsets, the microbiology saliva and microbiology dental plaque subset. These subsets will be based on the subjects who received study drug (C16G2 Varnish or Placebo) and have at least a baseline and one post-baseline saliva and dental plaque sample.

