Microbiology:	
All stimulated saliva and dental plaque samples obtained in this study will be tested for S. mutans using mitis-salivarius bacitracin (MSB) agar plating. Stimulated saliva and dental plaque samples taken at Visits 3 and 6 will be tested for total bacteria testing using Todd Hewitt (TH) agar plating. All dental plaque and stimulated saliva samples will be stored upon receipt for S. mutans and total bacteria testing using quantitative Real-Time Polymerase Chain Reaction (qRT-PCR) and bacterial community analysis.
 
At the screening visit, only stimulated saliva samples will be collected and tested for S. mutans Colony Forming Units (CFUs) to determine the inclusion criterion of $\geq 1 \times 10^5$ CFU/mL at Screening using MSB agar plating. At all other visits both stimulated saliva and dental plaque samples will be obtained for microbiology assessments. Samples will be collected at the following visits: Screening Visit 1, prior to dental prophylaxis at Visit 2, prior to study drug administration at Visits 3-5, follow-up Visits 6-10. For details refer to Appendix C.
																				

	Samples will be shipped overnight to the Sponsor's microbiology laboratory for analysis. Screening S. mutans results will be provided to the study center within 5 days of sample receipt.

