	
information on the safety and microbiology of multiple administrations of C16G2 Varnish or Placebo. Subjects may be replaced at the Sponsor's discretion.
 
Data Analysis:
 
Analysis Sets: There will be two analysis sets; the safety analysis set and the microbiology analysis set
 
• The safety analysis set will be defined as those subjects who received any amount of study drug (C16G2 Varnish or Placebo)• The microbiology analysis set will be comprised of two subsets, the saliva microbiology and dental plaque microbiology subset. These subsets will be based on the subjects who received study drug and have at least one baseline and one post-baseline dental plaque and saliva sample, respectively. 
Safety:
 
All safety-related interventions, adverse events (AEs), and findings will be summarized. The incidence and duration of treatment emergent AEs (TEAEs) will be summarized by study arm. An AE will be considered treatment emergent if the onset date and time occur on or after the recorded clock time of the administration of study drug (C16G2 Varnish or Placebo). Adverse events will be coded using the Medical Dictionary for Regulatory Activities (MedDRA®). The severity of each adverse event will be determined using the Common Terminology Criteria for Adverse Events (CTCAE) Version 4.0.
 
All adverse events (AEs) will be classified by the relationship of the event to study drug as 1) None, 2) Unlikely, 3) Possible or 4) Probable. All AEs will be followed in accordance with good medical practice until resolved or fully stabilized. All serious AEs (SAEs) will be followed until the outcome is known or the subject's condition has stabilized.
 
Other safety assessments include vital signs, oral cavity assessments, and targeted physical exams. These safety parameters will be presented using descriptive statistics.
 
Microbiology:
 
All stimulated saliva and dental plaque samples obtained in this study will be tested for S. mutans using mitis-salivarius bacitracin (MSB) agar plating. Stimulated saliva and dental plaque samples taken at visits 3 and 6 will be tested for total bacteria testing using Todd Hewitt (TH) agar plating. Dental plaque and stimulated saliva samples will be stored for S. mutans and total bacteria testing using quantitative Real-Time Polymerase Chain Reaction (qRT-PCR) and bacterial community analysis.
 
Descriptive statistics utilizing mean, standard deviation, median and range of S. mutans and total bacteria will be determined and compared to Baseline samples, as applicable.

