1.5.6 Microbiology Evaluations

1.5.6.1 Dental Plaque Sample Collection

A dental plaque sample will be collected using an interdental brush for the analysis of microbial populations and for quantification of *S. mutans* according to the Schedule of Microbiology Assessments in Appendix C.

Subjects will be instructed to swallow the saliva in their mouths. Subjects will be instructed to open their lips in a wide smile with teeth loosely together and suck in several times to remove bulk saliva from occlusal surfaces of the teeth. Study staff will sample the occlusal surface of molars and bicuspids in four quadrants of the subjects mouth with one interdental brush used for each

quadrant. Plaque collected from each interdental brush will be dispersed into one tube containing TH media.

Immediately after collection, dental plaque samples will be stored at 2-8°C. At the end of each day, all samples will be placed in an insulated box with ice packs, and a temperature monitoring device then shipped overnight for next day early morning delivery to C3 Jian. The study center will provide C3 Jian with pre-notification of the upcoming shipment by supplying a sample inventory list via email to:

[name]
Director of Product Development
C3 Jian, LLC
E-mail: [contact]
Office [contact] [name]
E-[contact]

A copy of the sample inventory list should also accompany the actual shipment. A template for preparation of the sample inventory list is provided in the Study Manual for the study. The minimum required sample shipping information includes; subject number, sample description, sample collection date & time, and the total number of samples in the shipment. Shipments of stimulated saliva and dental plaque samples will be combined.

For details on laboratory and shipping procedures refer to the Study Manual.

Upon arrival at C3 Jian, samples will be inventoried and entered into a database for tracking through the analysis process. Plaque samples will then be re-suspended and aliquoted for immediate processing for plating. Remaining plaque samples will be aliquoted in sterile labeled sample tubes and stored at -80°C for qRT-PCR analysis and/or bacterial community analysis.

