6.3.6.3 Clinic Visit 3 (Baseline, Day 0)

Subjects will be scheduled for this visit between 6AM and 10AM. Subjects should not be exposed to study drug if they present with any disruption or loss of integrity in the oral cavity mucosa, gingiva or have lip lesions, (e.g. aphthous stomatitis, active herpetic sores, cheek bites, severely chapped or cracked lips, etc.).

Pre-Dose

- Confirmation of eligibility
- Medical/Dental and Surgical History & Concurrent Illness Update
- Concomitant Medications Update
- Urine Pregnancy Test (females of childbearing potential only)
- Oral Cavity Assessment
- Targeted Physical Exam (general, extraoral, head & neck)
- Vital Signs (blood pressure, heart rate, temperature) taken in supine or sitting position
- Microbiology (stimulated saliva and dental plaque collection)
Note: Samples need to be obtained prior to oral hygiene
- Randomization
- Oral Hygiene (including brushing and flossing will be conducted at the clinic prior to study drug administration)

Study Drug Administration:

Instructions for the preparation of C16G2 Varnish or Placebo are provided in the Study Manual. Instructions for the application of study drug are provided in Appendix G.

- At Visit 3/Day 0, subjects will receive a single study drug administration. Subjects will have C16G2 Varnish or Placebo applied to all tooth surfaces.
Note: C16G2 Varnish or Placebo will not be actively removed, but remain on the subject's teeth until removed through normal wear and mastication after discharge

Post-Dose

- Photographic imaging immediately after study drug application (see instructions in Appendix H)
- Oral Cavity Assessment (hard and soft tissues)
- Vital Signs (blood pressure, heart rate, temperature) taken in supine or sitting position 1 hour (\pm 15 minutes) post study drug administration
- Subjects will not eat, swish, or drink anything besides plain water from study drug administration to one hour after study drug application. In addition, subjects will be advised to relax their jaws and to not grind their teeth. Subjects will be supervised to ensure compliance
- Adverse Events
- Discharge

6.3.6.4 Clinic Visit 4 (24-48 hrs Post Visit 3) & Visit 5 (24-48 hrs Post Visit 4)

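### The synopsis and Section 8.5 define the saliva and plaque microbiology subsets differently, and read literally neither ties each subset to its own specimen

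*Combined protocol and SAP*

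**What the plan says.** The synopsis (Statistical Methods, Analysis Sets) and Section 8.5 both split the microbiology analysis set in two.

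- Synopsis: "two subsets, the saliva microbiology and dental plaque microbiology subset". Membership is for dosed subjects who "have at least one baseline and one post-baseline dental plaque and saliva sample, respectively".
- Section 8.5: "two subsets, the microbiology saliva and microbiology dental plaque subset". Membership is for dosed subjects who "have at least a baseline and one post-baseline saliva and dental plaque sample".

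The subset order is saliva then plaque in both places. The specimen order is plaque then saliva in the synopsis, and saliva then plaque in Section 8.5. Only the synopsis says *respectively*. Neither sentence names the baseline visit; Section 6.3.6.3 labels Visit 3 (Day 0) as Baseline. Section 8.7.6.5 leaves further microbiology detail to the SAP, and no separate SAP text is among the documents supplied.

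**The concern.** These sentences decide who enters the summaries for both secondary objectives. A programmer who follows the synopsis to the letter picks the saliva subset by looking at plaque samples. One who follows Section 8.5 to the letter, without reading a *respectively* into it, requires both specimens and obtains two identical subsets. The two programs give different denominators, and neither gives the set that the subset names suggest.

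Cohorts are small, with 8 C16G2 and 3 placebo subjects each (Section 5 table), so a single misplaced subject is visible in a table. A missing baseline for one specimen is conceivable. For plaque, for example, all four quadrants go into one container: "Plaque collected from each interdental brush will be dispersed into one tube containing TH media".

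**Working it through.** The plan states no figure on this point, so the check compares the rules case by case and then sizes the difference under assumed loss rates.

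**Inputs.** Baseline is taken as Visit 3 (Section 6.3.6.3). After screening and Visit 2, the synopsis (Microbiology) places collections "prior to study drug administration at Visits 3-5, follow-up Visits 6-10". Post-baseline collections therefore run from Visit 4 to Visit 10, which is 10 − 4 + 1 = 7 per specimen. Allocation is 8:3 in each cohort, and 3 × (8 + 3) = 33 agrees with the stated total.

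**Step 1. Remove one sample at a time under each rule.**

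| Sample missing | Section 8.5, both specimens required | Synopsis, literal | Specimen-matched |
|---|---|---|---|
| Visit 3 plaque | out of both subsets | out of saliva subset; kept in plaque subset with no plaque baseline | out of plaque subset only |
| Visit 3 saliva | out of both subsets | out of plaque subset; kept in saliva subset with no saliva baseline | out of saliva subset only |
| Any one sample, Visits 4 to 10 | in both | in both | in both |

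The last row holds because six other post-baseline samples of that specimen remain. After baseline, a subject drops out only if all seven samples of one specimen are missing.

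**Step 2. Share of data affected.** One needless placebo exclusion takes 1/3 of a cohort's placebo subjects. One needless active exclusion takes 1/8.

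**Step 3. Size under assumed loss rates.** The documents give no loss rate. Let p be the chance that any one sample is missing, independent and equal for the two specimens (an assumption). Then the chance of exclusion from a subset is:

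- specimen-matched: m = 1 − (1 − p)(1 − p⁷)
- both specimens required: a = 1 − [(1 − p)(1 − p⁷)]²

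At p = 0.05 the p⁷ term is negligible, so m = 0.05 and a = 1 − 0.95² = 0.0975. Expected exclusions out of 33 are 33 × 0.05 = 1.65 and 33 × 0.0975 = 3.22. The chance that at least one of 3 placebo subjects is excluded is 1 − 0.95³ = 14.3% and 1 − 0.9025³ = 26.5%.

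| Assumed p | Expected excluded of 33, matched | Expected excluded of 33, both required | At least 1 of 3 placebo excluded, matched | At least 1 of 3 placebo excluded, both required |
|---|---|---|---|---|
| 1% | 0.33 | 0.66 | 3.0% | 5.9% |
| 2% | 0.66 | 1.31 | 5.9% | 11.4% |
| 5% | 1.65 | 3.22 | 14.3% | 26.5% |
| 10% | 3.30 | 6.27 | 27.1% | 46.9% |

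Requiring both specimens roughly doubles exclusions. The literal synopsis rule behaves differently. With equal loss rates it excludes as many subjects as the matched rule, but the wrong ones. At p = 0.05, a subject is wrongly left out of the saliva subset with probability 0.05 × 0.95 = 0.0475, and wrongly kept in it with the same probability. The subset size could look right while the membership is wrong.

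**The case against.** The strongest reply is that specimen-matched subsets were plainly meant. Section 8.5 lists subsets and specimens in the same order and can be read distributively, saliva with saliva and plaque with plaque. Requiring both specimens would make two named subsets pointless, and the *respectively* in the synopsis shows that a per-specimen rule was in mind. This largely stands. It does not rescue the synopsis, whose order is reversed, and it leaves two sentences that do not agree.

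A reader might also infer several stronger things that the documents do not support:

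- *Any lost tube deletes a series.* Step 1 shows that only a missing baseline sample does so, or the loss of all seven later samples of one specimen. Even the baseline case assumes that Visit 3 alone counts. Visit 2 samples are also taken before dosing, and Sections 1.5.6.2 and 1.5.6.3 call the screening saliva count baseline. If an earlier sample could serve, one missing Visit 3 sample would exclude nobody.
- *An unreadable tube has the same effect.* Both sentences count samples, not results, so a collected but unreadable sample still qualifies.
- *A subject with no saliva baseline enters the saliva change table.* No change value can be calculated for that subject. The denominator and the by-visit summaries can be affected; the mean change cannot.
- *Precision falls by 17%.* In SD units, the standard error of an active-minus-placebo difference is √(1/8 + 1/3) = 0.677, and √(1/8 + 1/2) = 0.791 after one placebo loss. That is the worst case for a contrast the plan does not state, since Section 8.1 makes all analyses descriptive. Losing one active subject gives √(1/7 + 1/3) = 0.690 (+2%). If 9 placebo subjects were pooled (an assumption), one placebo loss would move √(1/8 + 1/9) = 0.486 to √(1/8 + 1/8) = 0.500 (+3%).

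Finally, Section 8.4 lets the sponsor replace subjects, and the SAP may settle the definitions. Neither can be relied on here: no rule links replacement to a missing specimen, and no separate SAP text is available.

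**Conclusion.** The definitions are wrong as written, and the severity is minor. The synopsis rule is transposed, Section 8.5 is ambiguous between a both-specimens rule and a matched rule, and nothing else in the documents resolves the conflict. The consequence arises only when a subject lacks the baseline sample of one specimen (or every later sample of it) while the other specimen is adequate. It then touches the denominators and content of the descriptive secondary microbiology summaries, by up to 1 of 3 placebo subjects in a cohort for each such subject, and by a smaller share if placebo is pooled. The primary safety set is unaffected, and no hypothesis test depends on this.

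Confidence is high on the wording conflict. The amount of data at risk is unknown: the Step 3 figures rest on assumed, independent loss rates and on Visit 3 as the only baseline. Saliva and plaque travel in combined shipments (Sections 1.5.6.1 and 1.5.6.2), so joint losses would bring the rules closer together than the table shows.

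**What to change.** Replace both sentences, in the synopsis and in Section 8.5, with one specimen-matched definition and carry it into the SAP:

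> Saliva subset: dosed subjects with a Visit 3 saliva result and at least one later saliva result. Plaque subset: dosed subjects with a Visit 3 plaque result and at least one later plaque result.

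Naming Visit 3 removes the doubt about which sample is baseline. Asking for a result instead of a sample settles how an unreadable tube is treated. The cost is this one definition in two places, with no new data, visits or samples. It should be fixed before any microbiology summary is programmed, because the sponsor's team is unblinded and reviews these data throughout (Sections 8.3 and 8.6).

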8.6 Interim Safety Analysis

There are no interim analyses planned; however, microbiology data will be reviewed by the Sponsor's assigned team in an ongoing manner throughout the course of the study.

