Treatment / Randomization	
Approximately 11 subjects will receive multiple doses of study drug (27.2 mg C16G2 Varnish or Placebo) applied with a small brush typically used in dental varnish administration (for details see Table below and Appendix A). The Sponsor will perform an unblinded microbiology review on an ongoing basis to determine whether to enroll additional subjects into the next dose cohorts (13.6 mg and/or 54.4 mg C16G2 Varnish or Placebo) or to terminate enrollment based on microbiology data.
 
After confirmation of study eligibility, subjects will be randomized at Visit 3 (Day 0) by authorized study staff according to the master randomization schedule from the Sponsor's study statistician. The randomization schedule and associated documentation will be kept in a secure location.
 
C3J16-V204-00 Study Drug Schedule
 
  
 C16G2 Subjects	Placebo Subjects	Mode of Application	Days of Study Drug Admin.	C16G2 (mg)	
   
 8	3	Varnish	3	13.6	
 
 8	3	Varnish	3	27.2	
 
 8	3	Varnish	3	54.4	
  
	C16G2 Subjects	Placebo Subjects	Mode of Application	Days of Study Drug Admin.	C16G2 (mg)	8	3	Varnish	3	13.6	8	3	Varnish	3	27.2	8	3	Varnish	3	54.4
C16G2 Subjects	Placebo Subjects	Mode of Application	Days of Study Drug Admin.	C16G2 (mg)																	
8	3	Varnish	3	13.6																	
8	3	Varnish	3	27.2																	
8	3	Varnish	3	54.4																	
Blinding/Unblinding	The study will be conducted in a single-blind, placebo-controlled manner. All study subjects will be blinded to the treatment assignment, while the Investigator, study staff/clinicians and the Sponsor's assigned team members (e.g., the Clinical Monitor and the Medical Monitor) will be unblinded as to whether subjects are receiving C16G2 or Placebo. C16G2 Varnish and Placebo will be packaged and labeled identical to ensure blinding.																				

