2. STUDY OBJECTIVES

Primary Objective

- To evaluate the safety and tolerability of multiple C16G2 Varnish administrations in adolescent and adult dental subjects

Secondary Objectives

- To assess the targeted antimicrobial activity of C16G2 Varnish applications as measured by a reduction in *Streptococcus mutans* in saliva and dental plaque
- To assess total bacteria in saliva and dental plaque post-study drug administration

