3.1 Blinding and Randomization

3.1.1 Randomization

The study will enroll subjects into up to three study arms. Up to 33 subjects will receive multiple doses of study drug (27.2 mg and/or 13.6 mg and/or 54.4 mg C16G2 Varnish or Placebo) applied with a small brush typically used in dental varnish administration (for details see Appendix A). Subjects will be enrolled in an 8:3 ratio. The Sponsor will perform unblinded microbiology review on an ongoing basis to determine whether to enroll additional 11 subjects into the next dose cohort (13.6 mg and/or 54.4 mg C16G2 Varnish or Placebo) or to terminate enrollment based on microbiology data.

After confirmation of study eligibility, subjects will be randomized at Visit 3 (Day 0) by authorized study staff according to the master randomization schedule from the Sponsor's study statistician. The randomization schedule and associated documentation will be kept in a secure location at the study site.

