8.2 Randomization

The study will enroll subjects into up to three study arms. Up to 33 subjects will receive multiple doses of study drug (27.2 mg and 13.6 mg or 54.4 mg C16G2 Varnish or Placebo) applied with a small brush typically used in dental varnish administration (for details see Appendix A). Subjects will be enrolled in 8:3 ratio. A microbiology review will be conducted after all subjects in Arm 1 have completed Visit 8 (Day 14) and a determination will be made whether to enroll additional 11 subjects into Study Arms 2 and/or 3 (13.6 mg and/or 54.4 mg C16G2 Varnish or Placebo).

After confirmation of study eligibility, subjects will be randomized at Visit 3 (Day 0) by authorized study staff according to the master randomization schedule from the Sponsor's study statistician. The randomization schedule and associated documentation will be kept in a secure location.

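### Section 8.6 says no interim analysis is planned, but an unblinded review decides whether two further dose cohorts open; its timing is inconsistent and it names no safety summary

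*Combined protocol and SAP*

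**What the plan says.** Section 8.6 (Interim Safety Analysis) states "There are no interim analyses planned". The same sentence goes on to disclose that a sponsor team will look at microbiology results continuously while the trial runs. It does not say that the review is unblinded or that anything depends on it.

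The Synopsis (Treatment / Randomization) does: "The Sponsor will perform an unblinded microbiology review on an ongoing basis to determine whether to enroll additional subjects into the next dose cohorts", meaning 13.6 mg and/or 54.4 mg, after about 11 subjects at 27.2 mg or placebo. Section 3.1.1 repeats this and gives the alternative, "to terminate enrollment based on microbiology data".

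Section 8.2 describes a single look: "A microbiology review will be conducted after all subjects in Arm 1 have completed Visit 8 (Day 14) and a determination will be made" on whether a further 11 subjects enter Arms 2 and/or 3.

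Section 2 gives one primary objective: "To evaluate the safety and tolerability of multiple C16G2 Varnish administrations in adolescent and adult dental subjects". Reduction of S. mutans and assessment of total bacteria are secondary. Section 8.1 makes all analysis descriptive.

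**The concern.** A review of unblinded results that settles how many subjects are enrolled and at which doses is an interim analysis in function, whatever it is called. Section 8.6 is where a reader would look for it, and that section gives neither its purpose nor its consequence.

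Two practical matters follow. First, the sections do not agree on when the look takes place, so those running the trial cannot tell from the text what must be complete before a further cohort opens. Second, every passage on the decision names microbiology alone. As written, a cohort at twice the Arm 1 dose (54.4 / 27.2 = 2) could open before anyone has summarised the primary-objective data from Arm 1 by treatment group.

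**Working it through.** **1. Sample size.** The Synopsis and Section 5 tables give three cohorts of 8 active and 3 placebo subjects: 3 × (8 + 3) = 33. This reproduces the maximum in Section 8.4.

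**2. Share of the trial that depends on the review.** After the first cohort of 11, 33 − 11 = 22 subjects remain, and 22 / 33 = 67%. Total enrolment is therefore 11, 22 or 33 depending on the review.

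**3. Timing.**
- Synopsis and Section 3.1.1: ongoing, unblinded, decides on cohorts.
- Section 8.6: ongoing, no decision mentioned.
- Section 8.2: one look, once all Arm 1 subjects have completed Visit 8, labelled Day 14.

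The Study Visit Schedule (Section 6.3.2 and Appendix D) allows the day to be checked. Visit 3 is Day 0, Visits 4 and 5 each follow the previous visit by 24 to 48 hours, and Visit 8 is 7 ± 1 days after Visit 5.
- Visit 5: earliest 0 + 1 + 1 = Day 2; latest 0 + 2 + 2 = Day 4.
- Visit 8, nominal: 2 + 7 = Day 9 to 4 + 7 = Day 11.
- Visit 8, with window: 9 − 1 = Day 8 to 11 + 1 = Day 12.
- Visit 9 (14 ± 2 days after Visit 5): 2 + 14 − 2 = Day 14 to 4 + 14 + 2 = Day 20.

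Day 14 is outside the Visit 8 range and at the start of the Visit 9 range. This uses the three dosing visits of the schedule. Sections 3 and 8.1 give other counts (five applications and six days), which must be reconciled separately.

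**4. Safety data available at that point.** Visit 8 is the last visit with scheduled safety assessments: oral cavity assessment, targeted physical examination and adverse event collection (Section 6.3.2, Appendix B). A look after Visit 8 would therefore have Arm 1's scheduled safety data in hand. Summaries by treatment group are already planned for treatment-emergent events (8.7.6.1), oral cavity findings (8.7.6.2) and vital signs (8.7.6.4). Section 8.7.6.3 plans no separate table for the targeted examination; clinically significant changes after dosing are recorded as adverse events.

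**5. What such a summary can show.** Arm 1 has 8 active subjects. With no events in 8, the one-sided 95% upper limit for the event rate is 1 − 0.05^(1/8) = 31.2%. The chance of seeing at least one event is 1 − (1 − p)^8. For assumed true rates p of 5%, 10% and 20% (the documents give none) it is 33.7%, 57.0% and 83.2%. The summary would inform the decision; it could not establish safety.

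**The case against.** The case for leaving the plan alone is substantial, and several parts of it stand.

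- A reader who stops at the first clause of 8.6 might infer that the plan hides the look. It does not: the same sentence discloses the microbiology review, and the Synopsis, 3.1.1 and 8.2 state the decision openly. What 8.6 lacks is the label, the consequence and a cross-reference.
- A reader might infer that only serious events reach the sponsor. Section 7.8 asks for adverse event as well as serious adverse event information to be sent to the Medical Monitor and sponsor, Section 7.1 puts all adverse events in the EDC system, and Section 9.2.3 has the Clinical Monitor review entries on an ongoing basis. Both monitors are unblinded (3.1.2).
- A reader might infer that the decision rests on S. mutans alone. The wording is microbiology data, which covers total bacteria by TH plating at Visits 3 and 6 (8.7.6.5).
- Choosing cohorts on microbiology has a stated rationale. Section 1.3 bases dose selection on depth of kill and selectivity, and Section 1.1.1 reports that all three varnish doses were given once to adults, 30 of them on active drug, with no drug-related treatment-emergent events.

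This narrows the point without removing it. Reviewing events one subject at a time is different from a summary by arm at the moment a cohort is opened. The earlier varnish study gave single doses to adults, whereas this one repeats the application and admits subjects from age 12. The timing conflict is untouched by any of these arguments.

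**Conclusion.** The point holds as a cheap improvement to the plan. The review is an interim look that decides enrolment of up to 22 of 33 subjects; its timing is stated in two incompatible ways, one tied to a day that does not match the visit; and no passage brings a cohort-level safety summary into the decision.

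A reader might go on to infer that type I error is inflated or that the final active–placebo contrasts are biased. The documents do not support that. Section 8.1 plans no hypothesis test, each cohort has its own 3 placebo subjects, and nothing suggests that Arm 1 would go unreported if enrolment stopped.

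The conclusion assumes that the visit schedule governs when Visit 8 falls. The Appendix A schematic is not shown in the text available, and Section 8.7.6.5 defers further microbiology detail to a SAP whose text could not be checked on this point.

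**What to change.** - **Section 8.6:** state that the Arm 1 review is an unblinded interim look that decides whether further cohorts open or enrolment ends, and cross-refer to 3.1.1 and 8.2.
- **Timing:** make the Synopsis and Sections 3.1.1, 8.2 and 8.6 agree on whether the decision is ongoing or taken once, and correct the mismatch between Visit 8 and Day 14.
- **Review packet:** list the microbiology data (S. mutans change from Visit 3 by arm, and total bacteria change from Visit 3 to Visit 6 by arm) together with Arm 1 summaries of treatment-emergent adverse events, oral cavity findings and vital signs. Targeted-examination changes enter as recorded adverse events.
- **Study report:** disclose that later cohorts were opened, or enrolment ended, on this review.

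The clinical criterion for proceeding is for the sponsor to set.

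The cost is protocol wording and one early run of mostly planned tables on 11 subjects. If circulation stays with the Investigator, site staff and assigned sponsor team members, who are already unblinded, no blinding is lost.
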